7.3 Safety

1) American Diabetes Association (ADA) Severe Hypoglycemic AE

A hypoglycemic AE will be classified as "ADA-severe" if the answer to the question "Was third party intervention required for this episode of hypoglycemia?" is Yes on the Hypoglycemia CRF page as mentioned in the ADA hypoglycemia position statement (3).

ADA Severe Hypoglycemic AE should not be confused with hypoglycemia AEs that are graded severe (Grade 3) per National Cancer Institute Common Terminology Criteria for Adverse Events (NCI CTCAE) grade (see Section 11.8.2.1).

2) Adverse Event Leading to Discontinuation of IP

An AE will be classified as an AE leading to discontinuation of IP if the answer to the question "Did the adverse event cause the subject to be discontinued from the study?" is Yes on the AE CRF page.

3) Hypoglycemic AE

An AE will be classified as a hypoglycemic AE if the answer to the question "Is this a hypoglycemic event?" is Yes on the AE CRF page.

4) Injection Site Reactions

Injection site reactions will be identified using the Medical Dictionary for Regulatory Activities (MedDRA) High Level Term = "Injection site reaction".

5) IP-related adverse events

An AE will be classified as related to IP if the relationship to study treatment is Possibly Related, Probably Related, or Definitely Related. Additionally, if the relationship is missing, then the AE will be deemed IP-related.

6) Persistent/Non-persistent Hypoglycemic AE

Hypoglycemic event with Time in hypoglycemia (see definition in Section 7.4) greater or equal to an hour (per CGM) would be classified as persistent. A hypoglycemic event with Time in hypoglycemia below an hour (per CGM) would be classified as non-persistent.

7) Symptomatic Hypoglycemic AE

A Hypoglycemic AE will be classified as symptomatic if the answer to the question "Was subject aware of symptoms?" is Yes on the Hypoglycemia CRF page.

8) Treatment-emergent adverse events

Treatment-emergent adverse event (TEAE) is an event that started or worsened in severity on or after the day of the first dose of IP but not more than 30 days after the subject's last dose of IP.

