6.3.2 Safety

- The incidence and severity of all treatment-emergent adverse events (TEAE) and the following subgroups:
 - Hypoglycemia, which will be fully documented in the Hypoglycemic Events Record, using data from subject report (symptomatic), FBG from central lab, study issued glucometer and CGM
 - SAEs, including fatal events
 - Adverse events leading to termination of the study treatment and/or early withdrawal from the study
 - IP-related AEs
 - Injection site reactions
- The incidence of clinically significant laboratory abnormalities
- The incidence of clinically significant abnormalities in electrocardiogram (ECG) and vital signs

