6.4 Exploratory Endpoints

- Retrospective CGM hypoglycemia rate
- Time in hypoglycemia and hyperglycemia event based on CGM data
- Relationship between plasma concentrations of insulin glargine, M1, and M2, and AIA titers

8) Diabetes Disease Duration

The duration of diabetes is defined as the number of years from the date of original diagnosis of Type 1 Diabetes Mellitus to the date of randomization (presented in full years):

$$(\text{date of randomization} - \text{date of Type 1 diagnosis} + 1)/365.25$$

If the date of Type1 Diabetes Mellitus diagnosis is partially missing, then the following imputation rules will be applied:

- Missing day, but month and year are present: the day will be imputed as the 1st of the month.
- Missing day and month but year is present: the day and month will be imputed as July 1, or date of consent, whichever is earlier.
- Date completely missing: no imputation will be done, and diabetes disease duration will also be missing.

9) QD Compliance Dosing Regimen

QD Compliance is where the answer to the question "Was the subject compliant with QD dosing since the previous visit?" is Yes on all Average Daily Dose of Study Drug CRF pages. If a subject does not answer Yes then they are marked as No in all associated outputs.

10) Double Average Daily Dose

Double Average Daily Dose is defined as having at least double the average daily dose compared to the first average daily dose after randomization at any subsequent average daily dose assessment.

11) Eligibility-Related Important Protocol Deviation (ERIPD)

Eligibility-related important protocol deviations are important protocol deviations coded to the Inclusion Criteria or Exclusion Criteria categories or Other category with deviation that has description "Inadequate source documentation that is required to support eligibility assessment". Site POL008 has been placed in this Other category and is used in this derivation as the deviation relates to documentation of eligibility. (refer to Appendix 4 Immunogenic- and Efficacy-Interfering Important Protocol Deviations for details).

12) End of Treatment visit

The End of Treatment visit (EOT) is defined as the scheduled visit labelled in data as 'Visit 9 Week 26/ End of Study'. This includes any subject who discontinues from treatment before visit Week 26 who has scheduled Visit 9 procedures performed at a EOT visit.

13) Exposure

- Duration of therapy (presented in weeks with one decimal place)

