7.4 Exploratory

1) Continuous Glucose Monitoring Device Day of Wear

The day of wear will be defined as starting exactly $(x-1)*24$ hours and ending $x*24$ hours after the time of the first assessment at the given visit, where x is the day of wear from 2 to 8 days.

2) Time in hypoglycemia

The time in hypoglycemia will be defined using the CGM data from days 2 through 8 of wear at each of the 3 visits where CGMs are applied as the sum of the time where the glucose value is <3.0 mmol/L.

PPS will be used for some sensitivity analyses (for example, the primary endpoint for immunogenicity [from Section 11.6.1.3] and HbA1c [from Section 11.7.1.3]).

A second Per Protocol Analysis Set (PPS2) will be composed of all subjects whose treatment assignment was randomized, who received at least 1 partial dose and do not have any immunogenicity-interfering important protocol deviations (IIIPD) as defined in Section 11.3 up to visit Week 26. A third Per Protocol Analysis Set (PPS3) will be composed of all subjects whose treatment assignment was randomized, who received at least 1 partial dose and do not have any efficacy-interfering important protocol deviations (EIIPD) as defined in Section 11.3 up to visit Week 26. Subjects in the PPS2 and PPS3 will be grouped according to actual treatment received. The PPS2 and PPS3 are larger and less restrictive analysis sets than the PPS and will be used for some sensitivity analyses for the primary endpoint for immunogenicity [from Section 11.6.1.3] and HbA1c [from Section 11.7.1.3], respectively.

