11.7.3 Exploratory Variables

11.7.3.1 Retrospective Hypoglycemic Rate

In addition to the analysis of hypoglycemic events from the AE data, a retrospective analysis of the CGM data will be performed to identify hypoglycemic events that may have gone unnoticed by the subject (Table 6, Analysis 1). A retrospective CGM-hypoglycemic event will be defined as anytime the glucose concentration decreases below the threshold of ≤ 3.0 mmol/L. This definition is supported by Seaquist et al (8). Multiple hypoglycemic events while a subject is wearing the CGM device may occur and are defined as having a glucose concentration that returns to > 3.0 mmol/L before decreasing below the threshold again. The number of hypoglycemic events detected between days 2 through 8 of CGM wear for each

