**Table 6: Listing of hypoglycemic event summaries and analyses**

Analysis description	Section Reference	Tables Associated
1. Summary of Retrospective Continuous Glucometer Monitor (CGM): Hypoglycemia Rate	Section 11.7.3.1	Table 14.3.3.4.1
2. Retrospective Analysis of Continuous Glucometer Monitoring (CGM): Time in Hypoglycemia, Hyperglycemia and Euglycemia	Section 11.7.3.2	Table 14.3.3.4.2
3. Overall Summary of Treatment-Emergent Adverse Events	Section 11.8.1	Table 14.3.2.1
4. Treatment-Emergent Adverse Events by System Organ Class, Preferred Term	Section 11.8.1	Table 14.3.2.2
5. Hypoglycemic Treatment-Emergent Adverse Events by System Organ Class, Preferred Term, and Maximum CTCAE Grade (based on lowest blood glucose values measured by test method)	Section 11.8.2.1	Table 14.3.2.6.1
6. Severe Hypoglycemic Treatment-Emergent Adverse Events by Preferred Term	Section 11.8.1	Table 14.3.2.7
7. Serious Hypoglycemic Adverse Events by Preferred Term	Section 11.8.3	Table 14.3.2.13
8. IP-Related Serious Hypoglycemic Adverse Events by Preferred Term	Section 11.8.3	Table 14.3.2.14
9. Summary of Symptomatic or Persistent Hypoglycemic Treatment-Emergent Adverse Events	Section 11.8.2	Table 14.3.2.17
10. Summary of Symptomatic or Persistent Hypoglycemic Treatment-Emergent Adverse Events by Site	Section 11.8.2	Table 14.3.2.18
11. Analysis of Hypoglycemic Treatment-Emergent Adverse Events	Section 11.8.2	Table 14.3.2.19
12. Summary of Reported ADA Hypoglycemic Treatment-Emergent Adverse Events	Section 11.8.2.2	Table 14.3.2.20
13. Overall Summary and Analysis of Treatment-Emergent Adverse Events by ERIPD Subgroup in SS, PPS2, and PPS3	Section 11.8.1	Table 14.3.2.21; 14.3.2.22; 14.3.2.23; 14.3.2.24
14. Maximum Post-baseline Fasting Glucose CTCAE Grade	Section 11.8.4.1	Table 14.3.3.4.16

Subject incidence of the following TEAEs will be tabulated by preferred term in descending order of frequency in the total column:

- CTCAE Grade \geq 3 TEAEs
- Hypoglycemic TEAEs
- CTCAE Grade 3 or Greater Hypoglycemic AEs
- IP-related TEAEs
- CTCAE Grade \geq 3 IP-related TEAEs
- Fatal AEs
- SAEs
- IP-related SAEs
- Serious Hypoglycemic AEs
- IP-related Serious Hypoglycemic AEs
- AEs Pertaining to Injection Site Reactions

A forest plot of the difference in incidence rates and CIs of TEAEs preferred terms with a $\geq 5\%$ difference in incidence between groups will be summarized. The 90% CIs will be computed using Wald method for risk difference without continuity correction.

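### Minor: SAP 7.3(6) classifies a single hypoglycemic AE as persistent by a term whose visible definition, in 7.4(2), is a total over the CGM wear period and not the duration of an event

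*SAP*

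**What the plan says.** **The label.** SAP 7.3, item 6, works one event at a time: "Hypoglycemic event with Time in hypoglycemia (see definition in Section 7.4) greater or equal to an hour (per CGM) would be classified as persistent". An event with less than an hour, again per CGM, is non-persistent. Item 3 of the same section identifies a hypoglycemic AE from a yes/no question on the AE page of the CRF, so the unit is one AE record.

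**The term it points to.** SAP 7.4, item 2, limits the data to wear days 2 to 8 and defines time in hypoglycemia as a quantity taken "at each of the 3 visits where CGMs are applied as the sum of the time where the glucose value is <3.0 mmol/L". The same quantity is an exploratory endpoint in Section 6.4, "Time in hypoglycemia and hyperglycemia event based on CGM data", and has its own output in Table 6, Analysis 2, "Time in Hypoglycemia, Hyperglycemia and Euglycemia".

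**The CGM event.** SAP 11.7.3.1 treats an event as occurring when glucose "decreases below the threshold of ≤ 3.0 mmol/L". Multiple events within one wear "are defined as having a glucose concentration that returns to > 3.0 mmol/L before decreasing below the threshold again". Section 7.3, item 6, does not refer to this rule.

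**Where the label is used.** In the visible text it feeds Table 6, Analysis 9 (symptomatic or persistent hypoglycemic TEAEs) and Analysis 10, "Summary of Symptomatic or Persistent Hypoglycemic Treatment-Emergent Adverse Events by Site".

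**The concern.** The thing being classified and the thing being measured have different units. Persistence is a property of one AE, but the definition that 7.3(6) cites returns one number per subject and wear period. A programmer who follows the cross-reference gives every hypoglycemic AE of a subject in the same wear period the same label, however long each one lasted.

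For an excursion inside wear days 2 to 8, the period total can never be shorter than the excursion's own time below the same cut. The error therefore runs one way: short events can be called persistent, but long ones are not missed.

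Hypoglycemia is the adverse event of special interest (protocol Section 11.3), so the tables describing it should be reproducible from the SAP. On the visible text, two competent programmers could produce different versions of Analyses 9 and 10.

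**Working it through.** No figure in the plan needs reproducing. The check sets the definitions side by side and then does arithmetic on the CGM recording grid.

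**1. Units**

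| Place | What is measured | Unit |
|---|---|---|
| SAP 7.3(3) and 7.3(6) | hypoglycemic AE, labelled persistent or not | one AE |
| SAP 7.4(2) | sum of time <3.0 mmol/L, wear days 2 to 8 | one subject, one wear period |
| SAP 11.7.3.1 | CGM event, ended by return to > 3.0 mmol/L | one excursion |

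The label needs the third kind of unit (an excursion, tied to an AE). The cross-reference leads to the second.

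**2. What reaches one hour under 7.4(2)**

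Inputs: one reading every 15 minutes (protocol 8.1); wear days 2 to 8, that is 7 days (SAP 7.4); cut at 60 minutes (SAP 7.3(6)).

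- Readings per day: 24 x 60 / 15 = 96.
- Readings per wear period: 7 x 96 = 672.
- Assumption: each reading below 3.0 counts as 15 minutes. No counting convention appears in the visible text.
- Low readings needed: 60 / 15 = 4. Share of the period: 4 / 672 = 0.6%.

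Example: four isolated low readings on four different days total 4 x 15 = 60 minutes. By 7.4(2), a hypoglycemic AE in that period is persistent. By excursion duration the longest dip is 15 minutes, so it is not.

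If time is instead counted between consecutive low readings, an isolated reading adds nothing. Four dips of two adjacent readings then give 4 x 15 = 60 minutes from 8 readings, 8 / 672 = 1.2%. The mislabelling remains, still with no dip longer than 15 minutes.

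**3. How much follow-up is exposed**

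- CGM is worn after screening and before Weeks 12 and 26. TEAEs start on or after the first dose (SAP 7.3(8)), so the two later wear periods are the on-treatment ones.
- On-treatment CGM days analysed: 2 x 7 = 14. Treatment days: 26 x 7 = 182.
- Share: 14 / 182 = 7.7% at most.

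**4. Which analyses use the label**

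Only Analyses 9 and 10 of Table 6, in the visible text. Symptomatic status comes from the Hypoglycemia CRF page. If those tables count an AE meeting either criterion, a wrong persistence label changes the count only for asymptomatic AEs. If they show persistent events on their own line, symptomatic AEs are affected there too. The negative binomial model in the SAP's adverse event analyses uses the number of hypoglycemia events and not persistence. The primary AIA analysis and the HbA1c analysis do not use it either.

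**5. The two thresholds**

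Section 7.4 counts time <3.0; 11.7.3.1 states its event threshold as ≤ 3.0. If 3.0 itself qualifies under 11.7.3.1, a dip whose lowest value is exactly 3.0 is a CGM event with zero time in hypoglycemia.

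**The case against.** **The intended meaning is fairly clear.** Section 7.3(6) attaches the time to the event, and 7.4(2) can be read as supplying only the data source and the cut-off. Event duration was probably intended. That stands as a reading of intent. But the SAP sends the programmer to a defined term of the same name, and that definition is a sum over days.

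**An event-level rule may exist elsewhere.** The cross-reference is to Section 7.4 as a whole. The rest of 7.4, Section 11.7.3.2, part of 11.8.2 and the table shells are not shown in the available copy. This stands. A reader might infer that the SAP has no event-duration rule, or no rule matching AEs to CGM excursions; the documents do not support that inference.

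**The CGM qualifier limits the reach.** It may confine the label to events with CGM data; SAP 6.3.2 describes hypoglycemia as documented "using data from subject report (symptomatic), FBG from central lab, study issued glucometer and CGM", so CGM is one source among several. A reader might infer that AEs without CGM data become non-persistent by default. The text does not say so: non-persistent also requires a CGM time under an hour.

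**The threshold difference is a separate matter.** A reader might infer that no event duration can be derived until <3.0 and ≤ 3.0 agree. That goes too far. Ending events at a return to > 3.0 and summing time <3.0 inside them gives a defined number, which is sometimes zero.

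**Conclusion.** The cross-reference is wrong as written in the visible text, and the grade is minor. Followed literally, it labels an AE persistent from scattered readings: 4 of 672 (0.6%) at 15 minutes per reading, or 8 of 672 (1.2%) in the example that counts time between adjacent low readings.

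The reach is small. Two descriptive tables use the label, CGM covers at most 7.7% of treatment days, and the same rule applies in both arms. The primary, HbA1c and hypoglycemia-rate analyses are untouched.

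A reader might infer that a sizeable share of hypoglycemic AEs would be mislabelled. The documents give no distribution of excursion lengths, no number of excursions per wear period and no share of asymptomatic events, so no such share can be stated. The verdict assumes that no item in the text not shown overrides 7.4(2). If one does, what remains is an incomplete pointer in 7.3(6).

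**What to change.** - In SAP 7.3(6), replace the reference to Section 7.4 with the duration of the individual continuous CGM excursion that corresponds to the AE, using the event boundary of 11.7.3.1 (return to > 3.0 mmol/L). If an event-level rule already exists in text not shown, point to it instead.
- Keep the wear-period sum of 7.4(2) for the exploratory time-in-hypoglycemia endpoint only.
- As a separate wording correction, reconcile <3.0 in 7.4 and ≤ 3.0 in 11.7.3.1 to one analysis threshold.

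The cost is one or two sentences in the SAP and a change to derivation code, on CGM data already collected. The downside is that few AEs will be classifiable for persistence, because CGM covers so little of the treatment period. Analyses 9 and 10 should be read with that in mind.

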7.4 Exploratory

1) Continuous Glucose Monitoring Device Day of Wear

The day of wear will be defined as starting exactly $(x-1)*24$ hours and ending $x*24$ hours after the time of the first assessment at the given visit, where x is the day of wear from 2 to 8 days.

2) Time in hypoglycemia

The time in hypoglycemia will be defined using the CGM data from days 2 through 8 of wear at each of the 3 visits where CGMs are applied as the sum of the time where the glucose value is <3.0 mmol/L.

PPS will be used for some sensitivity analyses (for example, the primary endpoint for immunogenicity [from Section 11.6.1.3] and HbA1c [from Section 11.7.1.3]).

A second Per Protocol Analysis Set (PPS2) will be composed of all subjects whose treatment assignment was randomized, who received at least 1 partial dose and do not have any immunogenicity-interfering important protocol deviations (IIIPD) as defined in Section 11.3 up to visit Week 26. A third Per Protocol Analysis Set (PPS3) will be composed of all subjects whose treatment assignment was randomized, who received at least 1 partial dose and do not have any efficacy-interfering important protocol deviations (EIIPD) as defined in Section 11.3 up to visit Week 26. Subjects in the PPS2 and PPS3 will be grouped according to actual treatment received. The PPS2 and PPS3 are larger and less restrictive analysis sets than the PPS and will be used for some sensitivity analyses for the primary endpoint for immunogenicity [from Section 11.6.1.3] and HbA1c [from Section 11.7.1.3], respectively.

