The FreeStyle Libre Pro Flash Monitoring System is approved by the EMA for people 18 years of age or older with diabetes. The FreeStyle Libre Pro Flash Glucose Monitoring System sensor, which requires 12 to 24 hours to calibrate itself after application, will be worn for 8 days and will record the interstitial fluid glucose every 15 minutes. Data from the 2nd through the 8th days of wear will be used for each analysis. The sensor will be blinded to the subject and no subject action will be needed. The subject will also be issued a Mealtime & Insulin Dose Record in which they will record the time of their meals, and insulin use. After 8 days, the subject may remove the sensor, place in the biohazard bag provided and bring it with them to the randomization visit. If the end of the 8-day continuous glucose monitoring (CGM) period coincides with the date of the randomization visit, the sensor can be removed at the visit. Subjects will bring both their Hypoglycemic Events Record and their Mealtime & Insulin Dose Record to the randomization visit.

Subjects who meet the study eligibility criteria will be centrally randomized 1:1 in an open-label fashion to receive either Gan & Lee Insulin Glargine or Lantus® for 26 weeks.

Randomization will be stratified by country. Subjects will continue using their bolus insulin

but will substitute IP for their basal insulin. The Sponsor will ensure that all insulins will be provided to all subjects regardless of medical insurance or reimbursement issues.

At the randomization visit (Visit 2), subjects will receive supply of insulin kits with IP and the Investigator or designee will train subjects on all study procedures and proper dose administration.

Subjects in both treatment groups will be assessed every 2 weeks after Visit 2 (randomization visit) through Week 22 (telephone call); and then at Week 26; they will attend a total of 9 clinic visits (the screening visit, the randomization visit, and at Weeks 2, 4, 8, 12, 16, 20, and 26), 2 brief visits during which a CGM sensor will be applied (8-10 days before the visits at Weeks 12 and 26), and they will be contacted by telephone at Weeks 6, 10, 14, 18, and 22. The Week 26 visit (Visit 9) will be the end-of-treatment visit.

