For the visits at Weeks 12 and 26, the subject will have worn the sensor for the 8-day CGM period before the visit, and the site staff will remove the sensor at the visit. The Investigator or designee will use the reader to retrieve the data from the sensor, and the 8-day Mealtime & Insulin Dose Record will be collected and reviewed. The data from the sensor does not have to be uploaded at the time of the visit, but the Investigator will retain each subject's sensor until it is confirmed the data have been successfully uploaded. Each sensor will be labeled with the subject and visit number and will be stored in a secure location until the end of the study after confirmation of successful upload.

Investigators and staff will review the FreeStyle Libre Pro Flash Glucose Monitoring System warnings and limitations and instruct subjects about the need to avoid medications and conditions that could interfere with the results.

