## **12.10 Exploratory Variables**

The retrospective CGM hypoglycemic rate and time in hypoglycemia and hyperglycemia will be summarized for subjects in the Safety Analysis Set. The plasma concentrations of insulin glargine, M1, and M2 will be plotted against AIA titers.

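### SAP 7.4 defines CGM time in hypoglycemia as an unscaled sum; unless another section scales it by recorded time, lost sensor hours lower the value

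*SAP*

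**What the plan says.** SAP Section 7.4, item 2, first sets the window: "The time in hypoglycemia will be defined using the CGM data from days 2 through 8 of wear". The window applies separately to each of the three wear periods (screening, Week 12 and Week 26). Within it, the quantity is calculated "as the sum of the time where the glucose value is <3.0 mmol/L". Item 1 of the same section fixes each day of wear as a 24-hour block on the clock, "starting exactly $(x-1)*24$ hours and ending $x*24$ hours after the time of the first assessment", regardless of how much was recorded in it.

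On recording, Protocol 8.1 says the sensor "will be worn for 8 days and will record the interstitial fluid glucose every 15 minutes". For Weeks 12 and 26, Protocol 8.6.2 assumes a complete 8-day wear that ends with removal by staff at the clinic.

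The endpoint is exploratory. SAP 6.4 lists it as "Time in hypoglycemia and hyperglycemia event based on CGM data". Protocol 12.10 plans description only: "The retrospective CGM hypoglycemic rate and time in hypoglycemia and hyperglycemia will be summarized for subjects in the Safety Analysis Set". It gives no unit or denominator.

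SAP Table 6 (Analysis 2) places the analysis of time in hypoglycemia, hyperglycemia and euglycemia in Section 11.7.3.2. SAP 7.3, item 6, also cites the 7.4 definition to class a hypoglycemic event as persistent when it reaches one hour by CGM.

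**The concern.** A sum over a fixed window measures hypoglycemia only if the whole window was recorded. Under the 7.4 wording a sensor that stops early yields a smaller total, and nothing in that definition separates this from a subject with less hypoglycemia. The measure then reflects sensor survival as well as glucose.

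Two readings are at stake: change across the screening, Week 12 and Week 26 wear periods, and the comparison of arms at each period. Either can shift because recording time shifted.

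The SAP recognizes this issue elsewhere. Its negative binomial model for hypoglycemic adverse events (Table 6, Analysis 11) uses log follow-up time as an offset so that unequal exposure does not distort the rate. The 7.4 definition has no counterpart.

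**Working it through.** The documents give no expected value, variability or minimum wear for this endpoint, so there is no plan figure to reproduce. The check is how the defined quantity responds to lost recording.

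**Inputs from the documents**
- Window: wear days 2 to 8, so 7 × 24 = 168 hours (SAP 7.4).
- Sampling: every 15 minutes, so 96 readings a day and 7 × 96 = 672 in a full window (Protocol 8.1).

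**Assumptions, not in the documents**
- True share of time below 3.0 mmol/L, p: 1% to 6%.
- Hours lost, L: 0 to 84, lost at random with respect to glucose.

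**Formulas**
- Unscaled sum = p × (168 − L).
- Relative bias = p(168 − L)/(168p) − 1 = −L/168, whatever p is.
- Scaled value = sum ÷ (168 − L) = p.

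**One wear period**

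| Hours lost | Sum at p = 1% | Sum at p = 4% | Sum at p = 6% | Bias of sum | Scaled value at p = 4% |
|---|---|---|---|---|---|
| 0 | 1.68 h | 6.72 h | 10.08 h | 0 | 4.0% |
| 24 | 1.44 h | 5.76 h | 8.64 h | −14.3% | 4.0% |
| 48 | 1.20 h | 4.80 h | 7.20 h | −28.6% | 4.0% |
| 84 | 0.84 h | 3.36 h | 5.04 h | −50.0% | 4.0% |

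**Two arms with the same true share, p = 4%**
- Mean loss 12 h in both: 6.24 h and 6.24 h. No false difference.
- Mean loss 12 h and 24 h: 6.24 h and 5.76 h. False difference 0.48 h, ratio 144/156 = 0.923.
- Mean loss 12 h and 48 h: 6.24 h and 4.80 h. False difference 1.44 h, ratio 120/156 = 0.769.

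The ratios do not depend on p. The differences in hours do: for p from 2% to 6% they run from 0.24 to 0.72 h in the second case and from 0.72 to 2.16 h in the third.

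**Can the documents produce short recording?**
- *Baseline.* Protocol 9.1 allows screening from Day −14 to Day −1, and Protocol 9.2 collects the sensor at randomization. If the gap is g days, with g at most 8, and the sensor is collected at the same clock time, (g − 1) × 24 hours are usable: 72 of 168 for g = 4, 144 of 168 for g = 7. Protocol 8.1 describes two weeks between the visits, so a short gap is possible rather than typical.
- *Weeks 12 and 26.* Protocol 9.6 places application 8 to 10 days before the visit. Part of wear day 8 is lost only when the gap is exactly 8 days and removal falls earlier in the day than application. As an illustration, application at 15:00 and removal at 09:00 loses 6 of 168 hours, or 3.6%. A gap of 9 or 10 days loses nothing this way.
- *Early sensor failure or detachment.* This is possible in any period; the documents give no rate.

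**The case against.** The strongest objection is that a variable definition is not the analysis. A reader might infer from 7.4 that the plan never divides by recorded time and therefore counts lost hours as hours free of hypoglycemia. The documents do not support that. The text available lacks Section 11.7.3.2, Section 11.7.3.1 breaks off just before it, Section 7.4 is cut after item 2, and the table shells are in a separate document. A denominator or wear rule could sit in any of these places, and its absence from the available text is not its absence from the plan. This stands, and it makes the point conditional.

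A reader might also infer that the comparison of arms is biased. That needs unequal loss, and nothing in the documents suggests it: both arms use the same sensor, and its readings are hidden from subjects. The protocol plans a descriptive summary, and no formal test of this endpoint appears in the available text. This also stands.

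Finally, replacing the definition outright with a percentage would leave the one-hour persistence rule in SAP 7.3, item 6, without the absolute time it needs. This is correct and shapes the fix.

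What the objection does not remove is the wording of 7.4 itself: a complete sentence that yields an unscaled sum, which a programmer could implement as it stands.

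**Conclusion.** The point holds as a conditional one, and it is minor. As defined in SAP 7.4, the quantity falls by L/168 for L hours lost at random, or 14.3% per lost day, and it carries any imbalance in recording time into comparisons between visits or arms. Whether this reaches the reported tables depends on Section 11.7.3.2 and the table shell. How large it would be depends on sensor loss, for which the documents give no figure; the hours lost and the shares below threshold used above are assumptions. Scaling removes the bias only when loss is unrelated to glucose. The primary and key secondary analyses do not use this measure.

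**What to change.** First check Section 11.7.3.2 and the shell for Table 14.3.3.4.2. If they already scale by recorded time, change 7.4 to match. If not:

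- For the exploratory summary, define time in hypoglycemia, hyperglycemia and euglycemia as the percentage of recorded day 2 to 8 readings that meet the threshold, or as minutes per recorded day.
- Show recorded time (out of 168 hours, or 672 readings) by arm and visit, so that a reader can see any imbalance.
- Prespecify a minimum recording fraction for the main summary, and repeat the summary on all wear periods as a check. The documents offer no basis for a particular cut-off, so the sponsor should choose and justify it.
- Keep a separate absolute-time definition, under its own name, for the persistent-event rule in SAP 7.3, item 6. That rule applies to single events, which a total over a wear period does not describe.

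The cost is SAP wording and a revised derivation, using readings the trial already collects. The small downside is that some short wear periods leave the main summary.
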